### 6.3 Concomitant Medications

Outputs for concomitant medications will include any treatment reported on the “Concomitant Medications” form eCRF pages, with additional pages included as required per study. Prophylactic medication and premedication, such as anti-coagulant agents including aspirin and LMWHs, will be summarized separately.

#### 6.3.1 Corticosteroids

For any analyses requiring identification of corticosteroids we will use the company standard ‘corticosteroids’ drug basket created by the Drug Basket Committee (DBC) at: <http://we2.collaboration.roche.com/team/2012137a/SitePages/Default.aspx>. We will use the full list of terms from this basket.

For atezolizumab contained studies, impact of steroids on atezolizumab and IRR prevention will be explored.

### 6.4 Laboratory Data

Laboratory data that have been obtained will be converted to System International (SI) units. Grading system will be from NCI-CTC version 4. Where normal ranges are required to be converted, the Roche References Ranges will be used (cf. gcp\_spt000144). The grading will be defined as follows:

Project-specific Gradings:

Parameter	SI Unit	Grade 4 Low	Grade 3 Low	Grade 2 Low	Grade 1 Low
LYMPH	10**9/L	< 0.2	0.2 to < 0.5	0.5 to < 0.8	0.8 to < 1
NEUTR	10**9/L	< 0.5	0.5 to < 1	1 to < 1.5	1.5 to < 1.8
CRCL	mL/min	< 15	15 to < 30	30 to < 60	60 to < LLN

Parameter	SI Unit	Grade 1 High	Grade 2 High	Grade 3 High	Grade 4 High
LYMPH	10**9/L	-	> 4 to 20	> 20	-
NEUTR	10**9/L	-	-	-	-
CRCL	mL/min	-	-	-	-

#### 6.4.1 Hematology and Chemistry Laboratory Data

Summary tables will be produced for the hematology and chemistry laboratory parameters (LBCAT=HEMATOLOGY, LBCAT=CHEMISTRY).

#### 6.4.2 General Derivation Rules on Absolute Counts/Percentages

The laboratory parameters such as lymphocytes, eosinophils, basophils and monocytes might be recorded as absolute count or percentage in the eCRF. If on the same day and time, the absolute count

of the laboratory parameter is missing but the percentage is not missing, then the absolute count will be derived from the percentage to absolute count as follows:

ABSOLUTE\_COUNT = PERCENTAGE x WBC, where WBC is white blood cell (LBTESTCD=WBC) and expressed as cells per microliter (LBSTRESU =  $10^9/L$ , or  $10^3/uL$ ). Note that WBC values collected on the same date and time will be used in the derivation of absolute count. If the WBC value is missing on the same day and time then the absolute count of the laboratory parameter will also be missing.

Note: If a patient has multiple values of the same assessment on the same day and at the same time, the minimum values recorded will be retained for the calculation of the absolute counts.

### 6.4.3 Absolute Neutrophil Counts

Neutrophil count recovery is defined as absolute neutrophil count  $ANC \geq 1.0 \times 10^9/L$ , given ANC was collected after the patient has had his last dose of antibody, and  $ANC < 1.0 \times 10^9/L$  at the last previous visit before EOT. Neutrophil count recovery ( $ANC \geq 1.0 \times 10^9/L$ ) should not be immediately followed by  $ANC < 1.0 \times 10^9/L$ , or a missing assessment, but only by  $ANC \geq 1.0 \times 10^9/L$  at the next visit.

VISIT 1	VISIT 2	VISIT 3	VISIT 4	OUTCOME
$< 1.0 \times 10^9/L$	$\geq 1.0 \times 10^9/L$	missing	missing	Not RECOVERED
$< 1.0 \times 10^9/L$	$\geq 1.0 \times 10^9/L$	$\geq 1.0 \times 10^9/L$	$< 1.0 \times 10^9/L$	RECOVERED
$< 1.0 \times 10^9/L$	$\geq 1.0 \times 10^9/L$	$< 1.0 \times 10^9/L$	$< 1.0 \times 10^9/L$	NOT RECOVERED
$< 1.0 \times 10^9/L$	$\geq 1.0 \times 10^9/L$	missing	$< 1.0 \times 10^9/L$	NOT RECOVERED

Time to neutrophil count recovery is defined as the number of days between the date of last dose of antibody and the date of single recovery. In case a patient was not depleted at last dose of antibody, no time to single recovery will be calculated. Where no ANC value occurs at the last drug intake, the next valid ANC assessment will be taken. For instance, ANC values at the EOT visit might be used instead if there is no ANC assessment on the day of the last dose of the antibody. If there are multiple ANC records at a visit, the last ANC assessment will be retained provided there is a valid identifier. If a study does not have a valid identifier, the lowest ANC value at the visit will be used instead.

### 6.4.4 Serum Creatinine Clearance

Serum creatinine clearance will be derived using the Cockcroft-Gault formula (where needed).

### 6.4.5 Hy's Law Cases

Patients with ALT > 3x BL OR AST > 3x BL AND Total Bilirubin >2xULN within 14 days, at any time for post baseline measurement, will be investigated for potential Hy's Law cases in a patient listing.

A summary table showing the proportion of patients with elevated ALT, AST, ALP and Total Bilirubin will also be produced.

#### 6.4.6 B-Cell Depletion and Recovery

B-cell depletion is defined as CD19 B-cell count < 0.07x10^9/L and can only occur after at least one dose of antibody has been administered.

Time to depletion is defined as the number of days between the first intake of study drug and the date of first depletion (assessments at study day 1 after start of the infusion are considered as after baseline).

Note that CD19 B-cells with no time record are assumed to be collected before the first treatment dose. Hence B-cells with no associated time that are collected on the same day as the last dose of the antibody will be assumed to be pre-dose.

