#### 4.1.1 **Inclusion Criteria**

Patients must meet the following criteria for study entry:

- Signed Informed Consent Form
- Age  $\geq$  18 years
- Eastern Cooperative Oncology Group (ECOG) performance status of 0, 1, or 2 (see [Appendix 7](#))
- B-cell lymphoma classified as either of the following:
  - R/R FL after treatment with at least one prior chemoimmunotherapy regimen that included an anti-CD20 monoclonal antibody
  - Relapsed or refractory DLBCL after treatment with at least one prior chemoimmunotherapy regimen that included an anti-CD20 monoclonal antibody in patients who are not eligible for second line combination chemotherapy and autologous stem-cell transplantation, have failed second line combination chemotherapy, or experienced disease progression following autologous stem-cell transplantation
- Histologically documented CD20-positive lymphoma, as determined by a local laboratory
- FDG-avid lymphoma (i.e., PET-positive lymphoma)
- At least one bi-dimensionally measurable lesion ( $>$  1.5 cm in its largest dimension by CT scan or magnetic resonance imaging [MRI])
- Availability of a representative tumor specimen and the corresponding pathology report for retrospective central confirmation of the diagnosis of FL or DLBCL
  - If the archival tissue is unavailable or unacceptable, a pretreatment core-needle, excisional or incisional tumor biopsy is required. Cytological or fine-needle aspiration samples are not acceptable. Additional details are provided in [Section 4.5.6](#).
  - If a patient received anti-lymphoma treatment between the time of the most recent available biopsy and initiation of study treatment, a core-needle biopsy is strongly recommended.
- For women of childbearing potential: agreement to remain abstinent (refrain from heterosexual intercourse) *or use contraceptive measures, and agreement to refrain from donating eggs, as defined below:*
  - *Women must remain abstinent or use contraceptive methods with a failure rate of  $<$  1% per year during the treatment period and for at least 18 months after the last dose of study treatment for those treated with obinutuzumab, idasanutlin,*

*and venetoclax; and for at least 12 months after the last dose of study treatment for those treated with rituximab, idasanutlin, and venetoclax (see Section 5.4.3.1). Women must refrain from donating eggs during this same period.*

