#### **4.1.2 Exclusion Criteria**

Patients who meet any of the following criteria will be excluded from study entry:

- Known CD20-negative status at relapse or progression
- Prior allogeneic SCT
- Completion of autologous SCT within 100 days prior to Day 1 of Cycle 1
- Prior standard or investigational anti-cancer therapy as specified below:
  - Radioimmunoconjugate within 12 weeks prior to Day 1 of Cycle 1
  - Monoclonal antibody or antibody–drug conjugate within 4 weeks prior to Day 1 of Cycle 1

- Radiotherapy, chemotherapy, hormonal therapy, or targeted small-molecule therapy within 2 weeks prior to Day 1 of Cycle 1
- Clinically significant toxicity (other than alopecia) from prior therapy that has not resolved to Grade  $\leq 2$  (according to NCI CTCAE v4.0) prior to Day 1 of Cycle 1
- Grade 3b FL
- History of transformation of indolent disease to DLBCL (expansion-phase only)
  - History of transformation of indolent disease is allowed in the dose escalation phase.
- Central nervous system lymphoma or leptomeningeal infiltration
- Treatment with systemic corticosteroids  $> 20$  mg/day, prednisone or equivalent
  - Patients receiving corticosteroids  $\leq 20$  mg/day, prednisone or equivalent, for reasons other than lymphoma must be documented to be on a stable dose for at least 4 weeks prior to Day 1 of Cycle 1.
  - If corticosteroid treatment is urgently required for lymphoma symptom control prior to the start of study treatment, up to 100 mg/day of prednisone or equivalent may be given for a maximum of 5 days, but all tumor assessments must be completed prior to start of corticosteroid treatment.
- Clinical conditions requiring treatment with oral or parenteral anticoagulants or antiplatelet agents (e.g., chronic daily treatment with aspirin  $> 325$  mg/day, clopidogrel, warfarin, systemic low-molecular-weight heparin [LMWH]) unless treatment can be discontinued 7 days (or 5 half-lives) prior to initiation of study treatment (except used as flushes for indwelling catheters)
- Refusal of blood products and/or sensitivity to blood products
- History of severe allergic or anaphylactic reaction to humanized or murine monoclonal antibodies
- Known hypersensitivity or allergy to murine products or any component of the obinutuzumab, rituximab, idasanutlin, or venetoclax formulation

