##### 6.4.6.1 B-cell recovery

B-cell recovery is defined as CD19 B-cell count >= 0.07x10^9/L, and B-cell was collected after LAA, the patient's B-cells were previously depleted and recovery is not followed exclusively by further depletion, i.e. B-cell recovery at a visit cannot be immediately followed by B-cell depletion, or a missing assessment, but only by recovery at the next visit. Assuming the situation 4 B-cell assessments at 4 visits:

VISIT 1	VISIT 2	VISIT 3	VISIT 4	OUTCOME
DEPLETED	RECOVERED	missing	missing	Not RECOVERED
DEPLETED	RECOVERED	RECOVERED	DEPLETED	RECOVERED
DEPLETED	RECOVERED	DEPLETED	DEPLETED	NOT RECOVERED
DEPLETED	RECOVERED	missing	DEPLETED	NOT RECOVERED

Time to B-cell recovery is defined as the number of days between the date of LAA and the date of single recovery. In case a patient was not depleted at last dose of antibody, no time to single recovery will be calculated. Where no CD19 value occurs at LAA, the next valid CD19 assessment will be taken. For instance, CD19 values at the EOT visit might be used instead if there is no CD19 assessment on the day of LAA. If there are multiple CD19 records at a visit, the last CD19 assessment will be retained provided there is a valid identifier. If a study does not have a valid identifier, the lowest CD19 value at the visit will be used instead.

The Nadir is the lowest absolute CD19 value for the patient across all visits after baseline (assessment at study day 1 after start of the infusion is considered as after baseline). The time to nadir is the study

day of the earliest occurrence of the nadir value. In case of consecutive visits with the same value, the earliest date of assessments will be used. The time to nadir will be calculated as the study day of the earliest occurrence of the nadir value.

The parameters to be summarized will be CD19 + B-cell depletion and recovery over time, time to depletion, duration of depletion, time to recovery, and time to follow up without recovery.

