**Lower immunoglobulin thresholds:**

- IgA: 0.5 g/L
- IgM: 0.3 g/L
- IgG: 5 g/L

- **Depletion after Baseline:**
  - YES = (Lab value < Lower Threshold)
  - NO = (Lab value >= Lower Threshold)
  
- **Recovery:**
  - YES = (Lab value >= Lower Threshold), and the lab value was collected after the last dose of antibody and patient was previously depleted
  - NO = (Lab value < Lower Threshold) and the lab value was collected after the last dose of antibody and patient was previously depleted (only displayed for last value in patient listing)

Recovery (single) is the first recovery based on definition above which is not followed exclusively by further depletion i.e. recovery at a visit cannot be immediately followed by depletion, or a missing assessment, but only by recovery at the next visit. Time to single recovery is defined as the number of days between the date of last dose of antibody and date of single recovery. In case a patient was not depleted at the last dose of antibody no time to single recovery will be calculated. Where no immunoglobulin value occurs at the last dose of antibody, the next valid immunoglobulin assessment will be taken. If there are multiple immunoglobulin records at a visit, the last immunoglobulin assessment will be retained provided there is a valid identifier. If a study does not have a valid identifier, the lowest immunoglobulin value at the visit will be used instead. Recovery will be assessed up to the first day of NALT.

Analysis will be done separately for IgA, IgM and IgG. No time windows will be applied. Only visits with a valid date and non-missing values will be considered for the derivation of immunoglobulin recovery and depletion. Immunoglobulins with no associated time that are collected on the same day as the last dose of the antibody will be assumed to be pre-dose.

Descriptive statistics (n, mean, sd, median, range) will be produced at each timepoint where immunoglobulin values are available to describe the course of IgA, IgG and IgM.

An output will be produced to look at the proportion of patients with low immunoglobulin levels at each timepoint where immunoglobulin values are available.

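### The SAP's B-cell and immunoglobulin depletion rules ignore the baseline value, so patients who enter low and stay low are counted together with new on-study depletion

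*SAP*

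**What the plan says.** **B-cells (SAP 6.4.6).** Depletion is a CD19 count below 0.07x10^9/L that "can only occur after at least one dose of antibody has been administered". That clause sets a time, not a starting level. The SAP continues: "Time to depletion is defined as the number of days between the first intake of study drug and the date of first depletion". Recovery (SAP 6.4.6.1) is a count at or above the same limit, collected after the last antibody dose, in a patient who was previously depleted, and it must hold at the next visit.

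**Immunoglobulins (SAP 6.4.10.1).** The limits are IgA 0.5, IgM 0.3 and IgG 5 g/L. Depletion after baseline is scored "YES = (Lab value < Lower Threshold" and so on, again with no reference to the patient's own baseline. Recovery uses the same limits and again requires previous depletion. A time to recovery is defined, but no time to depletion.

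**Population (Protocol 4.1.1 and 4.1.2).** Both FL and DLBCL patients enter "after treatment with at least one prior chemoimmunotherapy regimen that included an anti-CD20 monoclonal antibody". The antibody washout is set by the exclusion "Monoclonal antibody or antibody–drug conjugate within 4 weeks prior to Day 1 of Cycle 1". The haematology exclusions cover haemoglobin, ANC and platelets. There is no CD19 or immunoglobulin criterion.

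**Sampling (Protocol Appendices 1 and 2).** Immunoglobulins and lymphocyte immunophenotyping are both drawn on Cycle 1 Day 1, and assessments on treatment days precede dosing unless stated otherwise. The next scheduled CD19 sample is Cycle 1 Day 15. The next scheduled immunoglobulin sample is at end of induction.

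**The concern.** A rule meant to describe depletion after baseline should separate a level that fell on study from one that was already low. Here the two are merged, in a population where a low starting level is foreseeable. All patients have had an anti-CD20 antibody, and Protocol 5.1.1 itself lists prolonged B-cell depletion among the important risks of obinutuzumab. Protocol 5.1.4.3 adds that NHL can be associated with impaired immune function.

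Three summaries are affected:
- the depletion rate, for both measures;
- time to depletion, for CD19 only;
- recovery, for both measures, because baseline-low patients count as previously depleted and so join the group in which recovery is judged.

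Protocol 2.1 makes change in clinical laboratory results a safety endpoint. Protocol 5.1.1.5 ties B-cell depletion to infection risk, so readers are likely to use these figures when interpreting infections. A rule that ignores baseline reports status rather than change.

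**Working it through.** The plan states no depletion rate, so there is no figure to reproduce. The check is of the rule and then of its arithmetic.

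**Step 1: follow a baseline-low patient through the rules.** Take a patient with CD19 below 0.07x10^9/L, or IgG below 5 g/L, before the first dose and at the first sample afterwards. The timing condition is met and the value is below the limit, so the patient is depleted. Nothing in SAP 6.4.6 to 6.4.10.1 excludes, flags or stratifies this patient. For CD19, time to depletion is the time to the first post-dose sample, about Cycle 1 Day 15 on the schedule, so it reflects the visit plan and not a fall in the count.

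**Step 2: the formula.** Inputs, neither of which is in the documents:
- q: share of patients low at baseline and still low after dosing (assumed 5% to 50%);
- p: risk of new depletion among the rest, taken as all starting at or above the limit (assumed 10% to 95%).

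Rate by the SAP rule: q + (1-q)p. Rate of new depletion among those at risk: p. Difference: q + (1-q)p - p = q(1-p). This is never negative, and it is zero only if q = 0 or p = 1.

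**Step 3: excess in percentage points, q(1-p).**

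| q | p = 10% | p = 20% | p = 50% | p = 95% |
|---|---|---|---|---|
| 5% | 4.5 | 4.0 | 2.5 | 0.25 |
| 10% | 9.0 | 8.0 | 5.0 | 0.5 |
| 25% | 22.5 | 20.0 | 12.5 | 1.25 |
| 50% | 45.0 | 40.0 | 25.0 | 2.5 |

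With p = 10%, and q = 10%, 20% and 40%:
- 0.10 + 0.90 x 0.10 = 19%
- 0.20 + 0.80 x 0.10 = 28%
- 0.40 + 0.60 x 0.10 = 46%

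**Step 4: in patients, for an expansion cohort of 40 (Protocol 6.1.2).** The SAP rule adds 40q patients to the count of new depletions.
- q = 25%, p = 20%: 10 + 30 x 0.20 = 16 of 40 (40%), against 6 of 30 (20%) newly depleted.
- q = 25%, p = 95%: 10 + 30 x 0.95 = 38.5 of 40 (about 96%), against 28.5 of 30 (95%). The rate barely moves, but 10 of the 38.5 were not new.

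The effect on the rate is therefore mainly a matter for immunoglobulins, where p may be modest. It is small for CD19 if nearly everyone depletes.

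**The case against.** The best defence is that the SAP defines a state, not a cause. Counting everyone below an absolute limit shows who is immunodeficient on study, which is a legitimate safety question. SAP 6.4.10.1 also asks for the proportion with low immunoglobulins at each timepoint with values. Day 1 samples exist, so the baseline share should be visible. These are single-arm descriptive summaries with no test or decision rule. Immunophenotyping is listed as an exploratory biomarker (Protocol Table 12), and neither low CD19 nor low immunoglobulin is an adverse event of special interest or a selected adverse event.

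Much of this stands and limits the weight of the point. It does not remove it. The by-timepoint table does not link a patient's baseline to later values, so it cannot separate new from pre-existing deficiency, and no output of the proportion already low at baseline is specified for CD19.

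A reader might infer more than the documents support:
- *That baseline-low patients show near-zero time to depletion.* On the schedule it is about 14 days, the same as for anyone newly depleted by the first post-dose sample. For immunoglobulins the SAP derives no such time.
- *That the SAP attributes all depletion to study treatment.* It does not say so; the labels are post-dose or after baseline.
- *That the 4-week washout proves patients enter low.* It is a minimum, and no baseline distribution is given.
- *That recovery should mean return to baseline, as in footnote w of Appendix 1 and footnote x of Appendix 2.* Those footnotes say when sampling may stop, and they offer the normal range as an alternative. Used as a definition, a patient with zero CD19 at entry and zero afterwards would count as recovered at once.

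**Conclusion.** The point holds in a limited form. Neither depletion rule has a baseline condition, and the eligibility criteria make low baselines foreseeable. Any rate built on these rules overstates new depletion by q(1-p) as soon as one patient enters low and stays low (and p is below 1). Over the assumed ranges the excess is 2.5 to 45 points for p of 10% to 50%, and 0.25 to 2.5 points for p of 95%. The true size cannot be worked out from the documents.

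Two limits apply. The SAP is shared across studies. Its introduction does not name BH39147, although its adverse event tables do, so the statement that every patient has had anti-CD20 therapy is made for this protocol only. The SAP also defers to a separate list of planned outputs that is not available here, and none of its 77 listed templates is a B-cell or immunoglobulin output, so the table layout cannot be checked. Sample size and the primary analysis are not affected.

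**What to change.** Add one sentence each to SAP 6.4.6 and 6.4.10.1:
- Derive new depletion, and for CD19 time to depletion, in patients whose baseline is at or above the limit.
- Report patients below the limit at baseline in a separate row, for CD19 and for each immunoglobulin.
- Show recovery split by baseline status, with the existing fixed limits and confirmation rule unchanged. Do not redefine recovery as return to baseline.

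The split of recovery also guards against a side effect of the sampling footnotes. A baseline-low patient whose sampling stops on return to baseline cannot later be seen to cross the fixed limit, and should not be read as a failure to recover from study treatment.

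The existing summaries of everyone below the limit can stay alongside. The cost is two sentences and some table rows. The Day 1 samples are already scheduled and SAP 2.3.3 already defines baseline, so no new data are needed.

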##### 6.4.6.1 B-cell recovery

B-cell recovery is defined as CD19 B-cell count >= 0.07x10^9/L, and B-cell was collected after LAA, the patient's B-cells were previously depleted and recovery is not followed exclusively by further depletion, i.e. B-cell recovery at a visit cannot be immediately followed by B-cell depletion, or a missing assessment, but only by recovery at the next visit. Assuming the situation 4 B-cell assessments at 4 visits:

VISIT 1	VISIT 2	VISIT 3	VISIT 4	OUTCOME
DEPLETED	RECOVERED	missing	missing	Not RECOVERED
DEPLETED	RECOVERED	RECOVERED	DEPLETED	RECOVERED
DEPLETED	RECOVERED	DEPLETED	DEPLETED	NOT RECOVERED
DEPLETED	RECOVERED	missing	DEPLETED	NOT RECOVERED

Time to B-cell recovery is defined as the number of days between the date of LAA and the date of single recovery. In case a patient was not depleted at last dose of antibody, no time to single recovery will be calculated. Where no CD19 value occurs at LAA, the next valid CD19 assessment will be taken. For instance, CD19 values at the EOT visit might be used instead if there is no CD19 assessment on the day of LAA. If there are multiple CD19 records at a visit, the last CD19 assessment will be retained provided there is a valid identifier. If a study does not have a valid identifier, the lowest CD19 value at the visit will be used instead.

The Nadir is the lowest absolute CD19 value for the patient across all visits after baseline (assessment at study day 1 after start of the infusion is considered as after baseline). The time to nadir is the study

day of the earliest occurrence of the nadir value. In case of consecutive visits with the same value, the earliest date of assessments will be used. The time to nadir will be calculated as the study day of the earliest occurrence of the nadir value.

The parameters to be summarized will be CD19 + B-cell depletion and recovery over time, time to depletion, duration of depletion, time to recovery, and time to follow up without recovery.

Disease progression will be taken into account in the summary of B-cell recovery: patients with PD before B-cell recovery or PD within 45 days after recovery will be accounted for in 'Recovery with PD'; other patients will be accounted for in 'Recovery without PD'. Time to B-cell recovery will be summarized separately for all patients and for patients who were in response at the time of recovery (no PD before or within 45 days from recovery). Patients with PD before recovery or within 45 days after recovery will be censored at the minimum of progressive disease date and B-cell recovery date.

B-cell depletion and recovery will be assessed up to the first day of NALT. Missing CD19 values might be recorded as "NOT DONE" or ".".

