- q Screening laboratory assessments may be used for Day 1 of Cycle 1 if performed within 24 hours prior to Day 1 of Cycle 1. Additional hematology and serum chemistry samples must be drawn 0–4 hours pre-dose and 8 and 24 hours post-dose on Day 1 of Cycle 1 to monitor for TLS. Note that the 24-hour post-dose sample will be obtained on Day 2 of Cycle 1.
- r Perform hematology and serum chemistry tests within 72 hours prior to Day 1 of each cycle and within 24 hours prior to Days 8 and 15 of Cycle 1. Samples for exploratory biomarker research should be collected at the same time as hematology and serum chemistry samples.
- s Includes sodium, potassium, glucose, BUN or urea, creatinine, calculated creatinine clearance, calcium, total bilirubin, direct bilirubin, total protein, albumin, ALT, AST, alkaline phosphatase, amylase, lipase, LDH, and uric acid.
- t All women who are not post-menopausal ( $\geq 12$  months of non-therapy-induced amenorrhea) or surgically sterile will have a serum pregnancy test at screening within 7 days prior to Day 1 of Cycle 1. Because of the suspected effect of idasanutlin or venetoclax on embryo–fetal development, monthly pregnancy testing is strongly recommended for women of childbearing potential.
- u Includes hepatitis B surface antigen, total hepatitis B core antibody, and hepatitis C virus antibody.
- v Perform at the same time as tumor assessments at 12, 18, and 24 months after initiation of induction treatment.
- w Perform every 3 months until recovery to either normal range or baseline level, disease progression, or the start of new anti-lymphoma treatment, whichever occurs first.

## Appendix 1

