### Schedule of Activities for Patients with Diffuse Large B-Cell Lymphoma: Dose-Escalation and Expansion Phases (cont.)

- x Perform every 3 months until recovery to either normal range or baseline level, disease progression, or the start of new anti-lymphoma treatment, whichever occurs first.
- y Refer to [Appendix 3](#) for detailed schedule.
- z Includes circulating lymphoma cells and/or cell-free circulating-tumor DNA.
- aa Includes B-cell counts (CD19), T-cell counts (CD3, CD4, and CD8), and natural killer cell counts (CD16 and CD56).
- bb Requires separate patient consent for RBR participation. Not applicable for a site that has not been granted approval for RBR sampling.
- cc Availability of adequate archival or freshly biopsied tumor tissue samples should be confirmed at screening (see Section [4.5.6](#) for details).
- dd A tumor biopsy sample is preferred and recommended at the time of progression unless no adequate tumor site is accessible.
- ee After informed consent has been obtained but prior to initiation of study treatment, only serious adverse events caused by a protocol-mandated intervention should be reported. After initiation of study treatment, all adverse events will be reported until 90 days after the last dose of study treatment. After this period, the Sponsor should be notified if the investigator becomes aware of any serious adverse event that is believed to be related to prior study treatment (see Section [5.6](#)). An exception is made for Grade 3 and 4 infections (related and unrelated) in patients who received obinutuzumab, which should be reported until up to 2 years after the last dose of obinutuzumab. The investigator should follow each adverse event until the event has resolved to baseline grade or better, the event is assessed as stable by the investigator, the patient is lost to follow-up, or the patient withdraws consent. Every effort should be made to follow all serious adverse events considered to be related to any of the study treatment components or trial-related procedures until a final outcome can be reported.
- ff The screening PET-CT scan must be performed within 35 days prior to Day 1 of Cycle 1.
- gg Perform only for patients who have received at least two cycles of induction treatment.

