
Brookmeyer and Crowley ([1982](#)). In addition, landmark estimates of the proportion of patients who are event free at 6 months, 9 months, 1 year, and 2 years will be provided, along with 95% asymptotic CIs using Greenwood's formula for standard errors.

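### Time to B-cell recovery is censored at progression, a competing event for recovery in response, with no stated scope or estimator; 1 minus Kaplan-Meier would overstate the chance of recovering before progression

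*SAP*

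**What the plan says.** SAP 6.4.6.1 defines recovery as a CD19 count back at or above the threshold after the last antibody dose in a patient who was previously depleted. It adds a confirmation rule: "B-cell recovery at a visit cannot be immediately followed by B-cell depletion, or a missing assessment, but only by recovery at the next visit".

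Patients with progression (PD) before recovery, or within 45 days after it, are tallied in a Recovery with PD category. Two time-to-event summaries follow: "Time to B-cell recovery will be summarized separately for all patients and for patients who were in response at the time of recovery". The next sentence is the censoring rule: "Patients with PD before recovery or within 45 days after recovery will be censored at the minimum of progressive disease date and B-cell recovery date". Assessment has a further limit: "B-cell depletion and recovery will be assessed up to the first day of NALT" (NALT is new anti-lymphoma treatment).

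No estimator is named for this parameter. SAP 5.3 names one for other endpoints only: "PFS, EFS, DFS, DOR, and OS will be summarized descriptively using the Kaplan-Meier method".

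For lymphocyte immunophenotyping in post-treatment follow-up, protocol Appendix 2 (footnote x, DLBCL) says: "Perform every 3 months until recovery to either normal range or baseline level, disease progression, or the start of new anti-lymphoma treatment, whichever occurs first". The FL rule, in Appendix 1 (footnote w), is the same.

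**The concern.** A patient who progresses leaves the post-treatment visits at which CD19 is scheduled, and can no longer recover while in response. For that target, PD, NALT and death prevent the event; they do not merely hide it. Censoring at PD treats these patients as if they would go on to recover at the rate of those still in response. One minus Kaplan-Meier then no longer gives the proportion who recover before PD.

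The second half of the rule is a different problem. A patient whose recovery was seen, and who progresses within the next 45 days, is censored on the recovery date. Whether that date counts as an event depends on what happens afterwards.

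Protocol 5.1.1 lists prolonged B-cell depletion among the important risks of obinutuzumab. An inflated recovery proportion makes that risk look smaller, and distorts any comparison between FL and DLBCL if their progression rates differ.

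**Working it through.** The documents give no recovery rate or probability, so there is no planned figure to reproduce. What follows is an illustration.

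**Inputs**
- Recovery after the last antibody dose: exponential, median 12 months. This is an assumption, varied below from 6 to 24 months.
- Progression: exponential and independent of recovery, with medians of 7 months (bendamustine-rituximab in relapsed/refractory DLBCL) and 29 months (obinutuzumab-bendamustine in relapsed/refractory indolent NHL). Both are PFS medians quoted in protocol 3.3.2.4.
- 45 days = 45/30.4375 = 1.478 months (conversion from SAP 2.3.9).
- NALT is not modelled separately.

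**Formulas**
- Hazards: r = ln 2/12 = 0.0578; p = ln 2/7 = 0.0990 or ln 2/29 = 0.0239 per month.
- Share of recoveries with no PD in the next 45 days: s = exp(−1.478p) = 0.864 or 0.965.
- SAP rule read as 1 minus Kaplan-Meier: 1 − exp(−r·s·t).
- Cumulative incidence of recovery before PD: r/(r+p) × [1 − exp(−(r+p)t)].

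**Results at t = 12 months**
- DLBCL-like: 1 − exp(−0.599) = 45.1%, against 0.368 × [1 − exp(−1.881)] = 31.2%. Excess 13.9 points.
- FL-like: 1 − exp(−0.669) = 48.8%, against 0.707 × [1 − exp(−0.980)] = 44.2%. Excess 4.6 points.

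**Separating the two parts of the rule.** Censoring at PD alone would give 1 − exp(−0.0578 × 12) = 50.0% in both cases, an excess of 18.8 and 5.8 points. The 45-day recoding takes back 4.9 and 1.2 points. The two parts act in opposite directions.

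**Other recovery medians, 12-month values (1 − KM against cumulative incidence before PD)**

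| Recovery median | DLBCL-like | FL-like |
|---|---|---|
| 6 months | 69.8% v 49.7% | 73.8% v 67.3% |
| 12 months | 45.1% v 31.2% | 48.8% v 44.2% |
| 18 months | 32.9% v 22.6% | 36.0% v 32.5% |
| 24 months | 25.9% v 17.7% | 28.4% v 25.7% |

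At 24 months with a 12-month recovery median, the gaps widen to 69.8% v 36.0% and 73.8% v 60.8%.

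**Dependence.** Simulating 400,000 DLBCL-like patients with recovery and PD times correlated (normal copula, 24 months) gives 50.9% v 30.1% at correlation +0.5 and 85.8% v 39.2% at −0.5. Recovery regardless of PD is 74.9% and 75.2% in those two cases. Against that other target, the SAP figure is therefore too low in one case and too high in the other.

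**How often the 45-day rule can act.** Follow-up samples are 3 months apart. After post-induction treatment, the end-of-treatment visit is 35 days after the last dose and the first follow-up visit 3 months after it: 3 × 30.4375 − 35 = 56 days. Both gaps exceed 45 days. PD within 45 days of a first recovery would usually come before the confirming sample, and sampling then stops. Under the confirmation rule that patient has not recovered and is simply censored at PD.

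**The case against.** The strongest reply is that the censoring sentence directly follows, and echoes, the definition of the in-response group. On that reading it governs only the in-response summary, and the all-patients summary is untouched. This is a fair reading, but the text does not say so, and it would not cure the in-response estimate, where PD competes with the event most directly.

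Several stronger readings are tempting and are not supported:
- A reader might infer that observed recoveries are erased. They are not; the Recovery with PD category keeps them. A tally, however, does not correct a time-to-event estimate.
- A reader might infer that the 45-day rule adds to the overstatement. It lowers the estimate, and if it dominated it could reverse the direction. Take 40 patients: 10 recover at month 6 and progress within 45 days, 10 recover at month 9 without PD, and 20 are censored at month 12. One minus Kaplan-Meier is 10/30 = 33%, while 20/40 = 50% recovered before PD and 10/40 = 25% recovered in response.
- A reader might say the rule estimates recovery in a world without progression. Even under independence it falls below that (45.1% against 50.0%).
- A reader might extend the point to immunoglobulins. SAP 6.4.10.1 has no censoring at PD.
- A reader might scale the excess by a standard error for 40 patients per disease. SAP 6.4.6.1 calculates time to recovery only for patients depleted at the last antibody dose, so 40 is not the right denominator.

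Three further replies stand as limits. Kaplan-Meier is inferred from the word censored. End-of-induction and end-of-treatment samples are not conditional on PD, so some recoveries after PD can be seen. And the SAP's own list of studies (section 1) omits BH39147, although its adverse-event tables include it.

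**Conclusion.** The concern holds in a limited form. The SAP states a rule that treats a competing event as ordinary censoring, without saying which summary it governs. If the result is reported as 1 minus Kaplan-Meier, it overstates the chance of recovering before PD in every exponential scenario examined: at 12 months by about 8 to 20 points with DLBCL-like progression and 3 to 7 points with FL-like progression.

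Those sizes are not estimates for this trial. The recovery medians are assumed, and the PFS medians come from other regimens and run from the start of treatment, not from the last antibody dose. That the bias would be larger in DLBCL is plausible on those figures but not established by the documents.

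The 45-day recoding is a separate fault of principle with little practical effect in follow-up. B-cell recovery is not a protocol endpoint and has no template among SAP Outputs 1 to 77, so the consequence is confined to an exploratory safety summary.

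**What to change.** In SAP 6.4.6.1:
1. State whether the censoring sentence governs the all-patients summary, the in-response summary, or both, and name the estimator and its target.
2. For in-response recovery, report the Aalen-Johansen cumulative incidence with PD, NALT and death as competing events.
3. In the all-patients summary, count every confirmed recovery up to NALT as an event on its own date.
4. Keep PD within 45 days after recovery as a descriptive split of recovered patients only.
5. Say how a recovery is confirmed when the protocol's sampling ends at recovery or at PD.

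The cost is SAP wording and a standard procedure; no new data are needed. The downside for the sponsor is that recovery percentages will be lower than 1 minus Kaplan-Meier would show.
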